11.2.2 Physical Examinations

A physical examination will be performed by a physician during screening and during the

24-hour follow-up safety assessment to assess possible changes in the subject's clinical condition.

The findings of each examination will be recorded on the appropriate CRF. Any physical examination finding that is classified by the investigator as a clinically significant worsening (i.e., that resulted in a change in subject management) compared to previous examination will be considered an AE, documented on the AE page of the CRF, and followed until resolution.

11.2.3 Vital Signs

Vital signs must be obtained and recorded, including:

- Systolic and diastolic blood pressure millimeters of mercury (mm Hg)
- Pulse rate (beats/minute)
- Respiratory rate (breaths/minute)

The same position and arm should be used each time vital signs are measured for a given subject.

Vital signs will be collected within 30 minutes prior to the Xe-133 imaging study. These will be considered baseline measurements. Additional vital signs will also be taken following completion of the Xe-133 imaging, but prior to Technegas imaging.

Vital signs will be taken at approximately 10 minutes (\pm 5 minutes) prior to Technegas inhalation and within 15 minutes following completion of the Technegas imaging. Additional vital signs will be taken during the 24-hour follow-up safety assessment.

The following changes (increases or decreases) in vital signs from pre-study baseline values are considered to be clinically significant and require commentary:

- systolic blood pressure > 45 mm Hg
- diastolic blood pressure > 30 mm Hg

Any clinically significant worsening changes will be documented on the AE page of the CRF.

11.2.4 Oxygen Saturation of the Blood using Pulse Oximetry

Oxygen saturation of the blood using pulse oximetry will be collected within 30 minutes prior to the Xe-133 study. This will be considered the baseline measurement. Oxygen saturation will also be taken following completion of the Xe-133 imaging, but prior to Technegas imaging.

Oxygen saturation will be taken at approximately 10 minutes (\pm 5 minutes) prior to Technegas inhalation and within 15 minutes following completion of the Technegas imaging. Additional oxygen saturation will be taken during the 24-hour follow-up safety assessment.

The investigator will assess and comment if oxygen saturation falls below 90%.
Attributability of any changes below 90% will be assessed as follows:

- 1 = Attributable to disease; no follow-up required
- 2 = Attributable to Xe-133 procedure; no follow-up required
- 3 = Possibly attributable to Technegas, FOLLOW-UP REQUIRED

Any oxygen saturation measurements with clinically significant changes below 90% and possibly attributable to Technegas will be repeated at appropriate intervals following the procedure until the values return to baseline or until the investigator and the Medical Monitor agree that further follow-up is no longer clinically relevant.

Any changes considered clinically significant and assessed as “3 = Possibly attributable to Technegas, FOLLOW-UP REQUIRED” will be documented on the AE page of the CRF.

11.2.5 24-Hour Follow-Up Safety Assessment

Subjects will return to the clinical site for a 24-hour follow-up safety assessment, to occur within 20 to 36 hours following the Technegas procedure. Subjects will undergo a physical examination, a blood draw for clinical chemistry and hematology laboratory measurements, vital signs (systolic and diastolic blood pressure, pulse rate, respiratory rate), pulse oximetry, and adverse event and concomitant medication assessments. Adverse event follow-up safety assessment will conclude at this visit if none are noted.

Any changes that the investigator feels are clinically significant should be noted and the investigator will comment on whether the change can be attributed to Technegas. If clinically significant changes are noted, appropriate follow-up will be conducted by the investigator as long as deemed necessary.

Investigators will make every effort to obtain the 24-hour assessment, as agreed to by the subject prior to enrollment.

However, if the subject is unable to return for the 24-hour safety assessment, the subject must be contacted by the Principal Investigator at 20 to 36 hours by telephone and interviewed for emergent adverse events. The telephone contact and results will be documented on the CRF and in subject records, including date, time and summary of conversation. If the subject cannot be reached by telephone, the Principal Investigator will attempt to contact the subject by mail or email to obtain information for emergent adverse events. All attempts to reach the

subject by telephone, or by mail or email if telephone communication cannot be established, must be documented in the subject's source records.

11.3 Adverse Events

An AE is any untoward medical occurrence in a subject administered an investigational drug, which does not necessarily have a causal relationship with the treatment. An AE can be any unfavorable or unintended sign (e.g., an abnormal laboratory finding), symptom, or disease temporally associated with the use of the study drug, whether or not it is considered to be study drug related. This includes any newly occurring event or previous condition that has increased in severity or frequency since the administration of the drug.

All AEs, ascertained through subject interview, physical examination or other means will be recorded on the AE page of the CRF. Adverse events will be recorded beginning at the time the subject signs the informed consent. Any AEs recorded before Technegas inhalation will be considered a pre-treatment AE.

11.3.1 Suspected Adverse Reaction

Suspected adverse reaction is any AE for which there is a reasonable possibility that the drug caused the adverse event. Suspected adverse reactions are the subset of all adverse events for which there is reasonable possibility that the drug caused the event. Reasonable possibility means there is evidence to suggest a causal relationship between the drug and the adverse event.

11.3.2 Adverse Reaction

An adverse reaction means any adverse event caused by a drug. Adverse reactions are a subset of all suspected adverse reactions for which there is reason to conclude that the drug caused the event.

11.3.3 Unexpected Adverse Events

An unexpected AE is any AE for which the specificity or severity is not consistent with the current Investigator's Brochure, the general investigational plan, or other product labeling.

11.3.4 Serious Adverse Events

A SAE is any AE, regardless of causality that:

- Results in death.
- Is life-threatening. Life-threatening means that the subject was at immediate risk of death from the reaction as it occurred, (i.e., it does not include a reaction which hypothetically might have caused death had it occurred in a more severe form).

- Requires subject hospitalization or prolongation of existing hospitalization. Hospitalization admissions and/or surgical operations scheduled to occur during the study period, but planned prior to study entry are not considered AEs if the illness or disease existed before the subject was enrolled in the trial, provided that it did not deteriorate in an unexpected manner during the trial (e.g., surgery performed earlier than planned).
- Results in persistent or significant disability/incapacity. Disability is defined as a substantial disruption of a persons' ability to conduct normal life functions.
- Is a congenital anomaly/birth defect.
- Is an important medical event. An important medical event is an event that may not result in death, be life-threatening, or require hospitalization but may be considered an SAE when, based upon appropriate medical judgment, it may jeopardize the subject, or may require medical or surgical intervention to prevent one of the outcomes listed in the definition for SAEs. Examples of such medical events include allergic bronchospasm requiring intensive treatment in an emergency room or at home, blood dyscrasias or convulsions that do not result in subject hospitalization, or the development of drug dependency or drug abuse.

In this subject population, hospitalization for lung disease, lung surgery, to treat pulmonary embolism (PE) or an underlying deep vein thrombosis (DVT) that may have caused PE is an expected event and actual admission may occur before or after a subject is enrolled in the study; therefore, hospitalization for lung disease, lung surgery or to treat DVT and/or PE which was the triggering factor for study enrollment will not be considered an SAE.

Planned hospital admissions or surgical procedures for an illness or disease which existed before the subject was enrolled in the trial or before study drug was given, are not to be considered AEs unless they occur at a time other than the planned date.

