11.4 Follow-up of Adverse Events

Subjects will return to the clinical site for a 24-hour follow-up safety assessment which will include an assessment of AEs. Any AE that is on-going at the time of the 24-hour follow-up assessment will be followed by the investigator until resolution or until the principal investigator and the Medical Monitor agree that further follow-up is no longer clinically relevant.

If subjects do not return for the 24 hour safety assessment, a follow-up telephone contact for AE resolution assessment must be documented on the CRF and in subject records, including

date, time and summary of conversation.

11.5 Procedures for Reporting AEs, SAEs and Suspected Unexpected Serious Adverse Reactions (SUSARs)

All AEs spontaneously reported by the subject and/or in response to an open question from study personnel or revealed by observation, physical examination or other diagnostic procedures will be recorded on the AE section of the CRF. Any clinically relevant deterioration in laboratory assessments or other clinical findings is considered an AE must be recorded on the AE section of the CRF.

All AEs will be noted and evaluated on the CRF with a full description of the nature, onset, duration, severity, attribution, and outcome of the event. All AEs will be coded using MedDRA. Any treatment used to alleviate the AE(s) will also be recorded.

Adverse event recording and reporting will conform to International Conference on Harmonisation (ICH) of Technical Requirements for Registration of Pharmaceuticals for Human Use Guidelines for Clinical Safety Data Management.

When possible, signs and symptoms indicating a common underlying pathology should be noted as one comprehensive event. All AEs should be recorded using standard medical terminology.

All SAEs that occur during the course of the study, as defined by the protocol, must be reported immediately by the investigator to the Medical Monitor by telephone or fax within 24 hours of the time the investigator first becomes aware of the SAE. Such preliminary reports should be followed with a detailed written description (within 5 days) which will include copies of hospital records and other documents when applicable.

All SAEs must be reported whether or not considered causally related to the study product. An SAE form will be provided to each clinical study site.

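### The SAE exemption for admissions due to the enrolling condition has no limit for worsening or timing, so an unplanned admission after Technegas for that condition can be classed as non-serious

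*Combined protocol and SAP*

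**What the plan says.** Section 11.3.4 of the protocol opens with "A SAE is any AE, regardless of causality that" meets one of a list of criteria, one of which is hospitalization or its prolongation. The section then treats hospitalization in three places.

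- **Hospitalization bullet.** Admissions or operations planned before study entry for an existing disease are not AEs, "provided that it did not deteriorate in an unexpected manner during the trial".
- **Population paragraph.** For the lung and thromboembolic conditions that bring subjects into the study, "actual admission may occur before or after a subject is enrolled in the study", and the rule given for SAEs is that "hospitalization for lung disease, lung surgery or to treat DVT and/or PE which was the triggering factor for study enrollment will not be considered an" event of that kind.
- **Closing paragraph.** Planned admissions or procedures for an illness that existed before enrolment or before study drug "are not to be considered AEs unless they occur at a time other than the planned date".

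Section 11.3 says of the AE definition: "This includes any newly occurring event or previous condition that has increased in severity or frequency since the administration of the drug". Section 11.5 requires SAEs to reach the Medical Monitor within 24 hours and adds that "All SAEs must be reported whether or not considered causally related to the study product". Section 11.5.1 makes seriousness one of three conditions for an IND safety report. Section 13.9 summarizes SAEs separately from other AEs. Section 5 names the safety profile of Technegas as a primary objective.

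**The concern.** Technegas is inhaled, and subjects are adults referred for ventilation scintigraphy. For many of them the condition that triggered enrolment is likely to be the one affecting the lungs or pulmonary circulation. If that condition worsens after inhalation and the subject is admitted, the reader needs to know whether this is an SAE. The general definition says yes, and the population paragraph says no. Two sites applying the same section could classify the same event differently.

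The label has consequences. Section 11.3.5 says that seriousness, not severity, guides regulatory reporting. An admission classed as non-serious has no 24-hour report and no SAE form, cannot meet the criteria for an IND safety report, and does not enter the SAE summary. Every subject receives both agents in a non-randomized design (section 6.2), so there is no concurrent group without Technegas in which a shortfall of classified events would show up.

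**Working it through.** No arithmetic applies: the plan states no expected number of SAEs and no precision target for them. The check sets the three exemptions side by side and then runs cases through them.

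| Exemption in 11.3.4 | Must be planned beforehand? | Exception attached | What is removed |
|---|---|---|---|
| Hospitalization bullet | Yes, before study entry | Unexpected deterioration during the trial | AE status |
| Population paragraph | No | None | SAE status |
| Closing paragraph | Yes | Not on the planned date | AE status |

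**Does the population paragraph reach admissions after Technegas?** It covers admissions after enrolment. Under section 6.4, enrolment comes first, then Xe-133, then Technegas. Admissions after Technegas are therefore inside it, and no other words in the paragraph take them out.

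**Case 1: unplanned admission after Technegas for worsening of the enrolling condition, no other seriousness criterion met.**
- Section 11.3: an AE, because a previous condition has increased in severity since the drug.
- Opening and hospitalization criterion of 11.3.4: an SAE, regardless of causality.
- Population paragraph: not an SAE.
- The two provisos do not help, because both qualify planned admissions only.

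The specific exemption overrides the general criterion, and the event is a non-serious AE.

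**Case 2: planned lung surgery for the enrolling condition, brought forward because the condition deteriorated unexpectedly.**
- Hospitalization bullet: the exemption is lost. Surgery performed early is the bullet's own example.
- Closing paragraph: the exemption is lost, because the date changed.
- Population paragraph: still not an SAE.

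Here the paragraphs contradict each other directly.

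**Case 3: admission after Technegas for a new condition.** The population paragraph does not apply, so the event is an SAE.

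**Case 4: the enrolling condition worsens and the event is fatal, life-threatening or disabling, prolongs an existing hospitalization, or is an important medical event.** The population paragraph speaks only of hospitalization and does not expressly exempt these criteria, so the event is still an SAE.

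**What follows in Case 1.** The 24-hour report and SAE form (11.5) are tied to SAE status. Section 11.5.1 says that an event failing any of its three conditions should not be sent as an IND safety report, and seriousness is one of them. The separate summary in 13.9 covers SAEs only. The event still counts among treatment-emergent AEs (13.8) and appears in the AE summaries by system organ class, relationship and severity (13.9). None of those summaries identifies it as an event that led to admission.

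**The case against.** The strongest reply is that the paragraph means only the index episode, that is, the admission belonging to the work-up for which the scan was ordered. Subjects may be scanned first and admitted hours later for what was already suspected, which would explain why admissions after enrolment are mentioned. Such an admission is not a drug effect, and exempting it is reasonable. The grammar allows this reading, since the triggering factor can be the hospitalization itself. But an admission that happens after enrolment cannot easily have triggered enrolment, so the text points at least as strongly to the disease. The objection shows that the wording is ambiguous, not that it is safe.

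Three stronger readings are tempting, and the documents do not support them.

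- A reader might infer that any unplanned respiratory admission after Technegas is not an SAE. Cases 3 and 4 show otherwise. The important-medical-event criterion does not depend on admission and gives bronchospasm needing intensive treatment as an example. It does rest on medical judgment, and an investigator may be slow to use it when the next paragraph calls the admission non-serious.
- A reader might infer that the bullet's deterioration proviso already makes the Case 1 admission an SAE. It does not, because it covers only admissions planned before entry. The conflict in Case 1 is with the general hospitalization criterion.
- A reader might infer that the event is lost, or that the SAE rate is understated by a calculable amount. The event is recorded as an AE with onset, severity, attribution and outcome (11.5). The documents give no count of such admissions and plan no confidence limit for an SAE rate.

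**Conclusion.** The concern holds in a narrow form. As written, section 11.3.4 allows an unplanned admission after Technegas for worsening of the enrolling lung disease, DVT or PE to be classed as non-serious when hospitalization is the only seriousness criterion met. In Case 2 the exemption also contradicts the two planned-admission paragraphs. What is at risk is the serious label and the reporting that depends on it, not the capture of the event.

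The size cannot be stated. SAP addendum section 2 reports 225 enrolled and 16 withdrawn before Technegas, leaving 225 − 16 = 209 subjects with complete data, but no document says how many were admitted afterwards. The number affected may be zero.

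The conclusion rests on reading the triggering factor as the disease. If it means the index admission only, the gap narrows, but the text should still say so. The point should be fixed because the change is specific and cheap and safety is a primary objective. It does not call the efficacy conclusions into question.

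**What to change.** 1. Reconcile the population paragraph of 11.3.4 with the hospitalization bullet, the closing paragraph and section 11.3. Limit the exemption to the index admission, meaning one under way or documented as decided before Technegas inhalation, and apply the section's existing deterioration proviso to it. Other admissions after Technegas for the enrolling condition would then follow the general hospitalization criterion, with causality assessed separately.
2. For subjects already dosed, search source records for admissions after Technegas that were excluded under this paragraph. List any that are found and present the SAE summary of section 13.9 with and without them. If none are found, say so in the report.

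**Cost.** The change in step 1 is a few sentences, but section 17.2 requires amendments to be submitted to FDA and the IRB/IEC and approved before use. The SAP addendum also notes that the protocol was agreed with FDA under a special protocol arrangement, so the change should be raised with FDA. Step 2 needs a source check and one extra table. The downside is some additional SAE forms for disease-related admissions and possibly a higher reported SAE count.

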11.3.5 Severity of Adverse Events

Severity is defined according to the following criteria:

Mild	Awareness of sign or symptom, but easily tolerated
Moderate	Discomfort enough to cause interference with normal daily activities
Severe	Inability to perform normal daily activities

The terms "serious" and "severe" ARE NOT synonymous. The term "severe" is often used to describe the severity of a specific event (as in mild, moderate, or severe myocardial infarction); the event itself, however, may be of relatively minor medical significance (such as a severe headache). This is NOT the same as "serious," which is based on subject/event

outcome or action criteria described above and are usually associated with events that pose a threat to a subject's life or functioning.

A severe AE does not necessarily need to be considered serious. For example, persistent nausea of several hours duration may be considered severe nausea but not an SAE. On the other hand, a stroke resulting in only a minor degree of disability may be considered mild, but would be defined as an SAE based on the above noted criteria. Seriousness (not severity) serves as a guide for defining regulatory reporting obligations.

11.3.6 Relationship to Study Drug

Relationship to study drug administration will be determined as follows:

None	No relationship between the experience and the drug; related to other etiologies such as concomitant medications or subject's clinical state.
Unlikely	The current state of knowledge indicates that a relationship is unlikely.
Possible	A reaction that follows a plausible temporal sequence from use of the drug and follows a known response pattern to the suspected drug. The reaction might have been produced by the subject's clinical state or other modes of therapy administered to the subject.
Probable	A reaction that follows a plausible temporal sequence from the use of the drug and follows a known response pattern to the suspected drug. The reaction cannot be reasonably explained by the known characteristics of the subject's clinical state or other modes of therapy administered to the subject.
Definite	A reaction that follows a plausible temporal sequence from use of a drug and follows a known response pattern to the suspected drug.

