13.9 Safety Analyses

The summary and analysis of safety data will be conducted on the modified ITT dataset.

Frequency distributions including counts and percentages will be used to summarize the qualitative safety data, including AEs, clinically significant changes in laboratory measurements and vital signs, and treatment emergent abnormalities in physical examinations. The summary of AEs will include summaries by MedDRA system organ class, relationship to study treatment, and event severity. Serious adverse events also will be summarized separately.

Summary statistics will be provided for all continuous safety data including change in laboratory measurements, vital signs and oxygen saturations. Paired t-tests will be used to test for statistically significant changes over time. The laboratory measurements at baseline and follow-up also will be categorized relative to their reference ranges as low, within range, or high, and shift tables comparing the distributions from baseline to follow-up will be provided for each test. The Stuart Maxwell test will be used to test for statistically significant changes in pre- versus post-treatment distributions.

14 Data Handling and Record Keeping

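### Section 11.3.6: any event meeting Possible or Probable also meets Definite, and a new type of reaction with plausible timing fits none of the three

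*Combined protocol and SAP*

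**What the plan says.** Section 11.3.6 of the protocol gives five levels of relationship to study drug: None, Unlikely, Possible, Probable and Definite. The top three, from the highest down, are defined as follows.

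- *Definite* is worded "A reaction that follows a plausible temporal sequence from use of a drug and follows a known response pattern to the suspected drug", and its entry stops there.
- *Probable* has the same two elements, timing and pattern, and then one more about other causes: "The reaction cannot be reasonably explained by the known characteristics of the subject's clinical state or other modes of therapy administered to the subject".
- *Possible* likewise has timing and pattern, but its extra clause points the other way: "The reaction might have been produced by the subject's clinical state or other modes of therapy administered to the subject".

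Unlikely applies where present knowledge points away from a relationship. None applies where there is no relationship and another cause accounts for the event. The section has no rule for choosing between two levels that both apply.

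The scale is used in two places. Section 11.5 asks the investigator to assess relatedness for each serious adverse event (SAE). Section 13.9 plans a table: "The summary of AEs will include summaries by MedDRA system organ class, relationship to study treatment, and event severity".

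Causality is also judged elsewhere in other terms. Sections 11.2.1 (laboratory values) and 11.2.4 (oxygen saturation) let the investigator code a change as possibly attributable to Technegas, and such changes go on the AE page when clinically significant. Section 11.3.1 defines a suspected adverse reaction by a reasonable possibility of causation. None of these mentions a known response pattern, and none is mapped to the five levels.

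**The concern.** A relatedness scale should become more demanding as it rises, and each event should have one place on it. Here the top level omits the question of other causes, which is the only thing that separates Possible from Probable.

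That question matters in this trial. Safety is a primary objective (section 5). There is no concurrent control group: every subject inhales Xe-133 and then Technegas, and section 6.2 accepts that the two may be confounded in the safety parameters. Sections 8.2 and 12.1 allow a perfusion study with another agent afterwards. Attribution therefore rests heavily on whether something else could explain an event.

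The known-pattern condition raises a second issue. A reaction not seen before with Technegas has, by definition, no known response pattern. Section 11.3.3 defines an unexpected event as "any AE for which the specificity or severity is not consistent with the current" Investigator's Brochure and related information, so the events the scale serves worst overlap with those the protocol classes as unexpected.

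**Working it through.** The plan states no figure on this point, so the check is one of logic. Each definition in 11.3.6 is coded on three yes/no conditions:

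- T: the timing is plausible.
- K: the event follows a known response pattern.
- A: the subject's clinical state or other therapy could reasonably explain it.

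On that coding:

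- Possible = T and K and A
- Probable = T and K and not A
- Definite = T and K

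There are 2 × 2 × 2 = 8 combinations.

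| T | K | A | Levels met among the top three |
|---|---|---|---|
| yes | yes | yes | Possible, Definite |
| yes | yes | no | Probable, Definite |
| yes | no | yes | none |
| yes | no | no | none |
| no | any | any | none (4 combinations) |

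Three results follow.

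1. Both combinations that reach the top three levels meet exactly two of them, and one of the two is always Definite. No combination meets Definite alone. Definite has 2 conditions and Probable has 3.
2. No combination meets three levels, because the added clauses of Possible and Probable oppose each other. This takes *might have been produced* and *cannot be reasonably explained* as opposites, which is their natural reading.
3. With K = no, none of the three levels can be reached, even when timing is plausible and no other cause is in view. None does not fit that last case, since it refers the event to another cause. Unlikely fits only if present knowledge argues against a relationship, and for a new reaction it may say nothing either way.

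Setting the sections side by side shows the conflict. Take a clinically significant laboratory change with plausible timing and no known pattern. Under 11.2.1 it can be coded as possibly attributable to Technegas and entered on the AE page. Under 11.3.6 the same AE fails Possible. Under 11.3.1 it may still be a suspected adverse reaction. The protocol gives no rule to reconcile the three.

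**The case against.** The labels are plainly ordered, and investigators will probably use them that way. The boundary between Possible and Probable is clear, so the overlap concerns only where Definite begins. The relationship table is one descriptive breakdown. The AE endpoint in 13.8 is incidence of treatment-emergent events, which does not use relatedness, and no test, success criterion or stopping rule depends on the scale. Pooling the top three levels as related removes the overlap. All of this stands and limits the size of the point. But ordered use would be custom, not something the protocol states, and pooling does not fill the gap for events without a known pattern.

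A reader might also infer three stronger things, which the documents do not support.

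- *One event can sit at three levels.* It cannot. Possible and Probable exclude each other, so the overlap is two levels at a time.
- *New reactions are pushed down to Unlikely.* The text does not direct that. Unlikely has its own condition, which such an event need not meet. The defect is a gap in the scale, not an instruction to downgrade.
- *Serious unexpected reactions will be missed.* Section 11.5 requires every SAE to be reported to the Medical Monitor within 24 hours, whether or not it is thought related. Under 11.5.1 the sponsor, with the Medical Monitor, applies a separate reasonable-possibility test that needs no known pattern and no level of the five-point scale. Expedited reporting is therefore largely protected.

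**Conclusion.** The point holds as a flaw in a stated rule. As written, 11.3.6 does not separate Definite from Possible or Probable, and it leaves a new type of reaction with plausible timing outside all three. It also conflicts with 11.2.1, 11.2.4 and 11.3.1.

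Its size is modest. It affects investigator attribution for AEs and SAEs and the AE summary by relationship in 13.9. Within that table, the split among the top three levels depends on how each assessor reads Definite, and the count of related events may omit reactions without a known pattern. The documents give no event counts, so the number affected cannot be stated. Sample size and all efficacy analyses are unaffected.

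The conclusion assumes that no other study document redefines the levels. SAP Version 2, the Investigator's Brochure and the CRF were not available. If any of them words the scale differently, it should be reconciled with 11.3.6.

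**What to change.** Rewrite 11.3.6 so that the levels are ordered and exclusive:

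- *Definite*: the Probable conditions, including that no other cause reasonably explains the event, plus a named confirming criterion chosen by the sponsor.
- *Probable*: as now, without that confirming criterion.
- *Possible*: remove the known-pattern requirement. State that an event with plausible timing but no known pattern is rated at least Possible, whether or not another cause could explain it.

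Dropping the pattern condition alone would not be enough. An event with plausible timing, no known pattern and no other explanation would still fail Possible, because the remaining clause says another cause might have produced it. With the added statement, each of the four combinations with plausible timing has one level: Possible for three, and Probable or Definite for the one with a known pattern and no other explanation.

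For AEs already recorded, wording alone is too late. The SAP addendum (sections 1 and 2) reports 225 enrolled less 16 withdrawn before Technegas, so 209 with complete data, and an interim safety report already submitted. Therefore:

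- keep the original ratings;
- present Possible, Probable and Definite pooled as related;
- list events rated None or Unlikely that had plausible timing, using the onset (11.5) and inhalation times (9.2) already collected;
- show any re-rating beside the original and label it post hoc, since the study is open-label.

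The cost is a protocol and CRF wording amendment with the FDA and IRB/IEC submission and approval that section 17.2 requires, under a protocol covered by a special protocol agreement, plus a limited AE review. The new rule for Possible may also raise the count of related events, because follow-up ends 20 to 36 hours after Technegas and many events will have plausible timing.
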